We plan to enroll 67 children with hematologic malignancies (including acute myeloid leukemia, acute lymphoblastic leukemia, juvenile myelomonocytic leukemia, and myelodysplastic syndrome) at the time of HSCT at three institutions (including UCSF, All Children's Hospital, St. Petersburg, FL, and Lucile Packard Children's Hospital, Palo Alto, CA). Patients will be enrolled on the study by day +28, prior to withdrawal of immunosuppression or administration of donor lymphocyte infusion (DLI). They will have donor chimerism and minimal residual disease (MRD) testing from the peripheral blood (PB) and bone marrow (BM) on day $+28 \pm 7$ (as per standard of care). Based on risk assessment, patients will receive one cycle of low-dose azacitidine ($40\text{mg}/\text{m}^2$ IV/SC daily $\times 4$ days) alone as immunosuppression is tapered. After tapering immunosuppression, chimerism will be repeated and patients will receive up to 6 additional cycles of low-dose azacitidine. For patients who meet at high risk for relapse, azacitidine will be combined with escalating doses of DLI for a maximum of 7 cycles in total. Risk and safety assessments, including routine laboratory parameters, donor chimerism, minimal residual disease, and GHVD activity will be assessed following each cycle.

The primary outcome measures will be indicators of relapse risk and safety / toxicity. Patients will be followed for relapse as well as incidence of severe drug toxicities and acute and chronic GVHD until 2 years post-transplant. The study will be considered successful if the rate of relapse at 2 years is $<25\%$, and the incidence of Grade IV GVHD and severe drug toxicity are $<20\%$. Correlative studies will include the effect of azacitidine on T cell immune reconstitution, as well as prospective minimal residual disease estimation by gene expression / mutation panels in patients with AML.

Study Schema

Standard Risk:

- Active Grade I GVHD, OR
- Any history of >Grade II GVHD, OR
- Full Donor Chimerism AND Pre-HSCT MRD-neg AND Post-HSCT MRD-neg

High Risk:

- No GVHD or resolved Grade I GVHD, AND
- Mixed chimerism OR Pre-Tx MRD(+) OR Post-Tx MRD(+)

[figure not shown]

Figure 1a: Schema for myeloid malignancies. Patients will be enrolled on study prior to Day +28. Chimerism from PB and BM as well as MRD will be assessed. Patients with Grade III-IV GVHD will not receive study immunomodulatory therapy. Patients meeting criteria for High-Risk designation will receive azacitidine followed by fast withdrawal of immunosuppression. Standard-Risk patients will receive azacitidine with standard withdrawal of immunosuppression. Risk assessment will be completed following withdrawal of immunosuppression, and patients will be assigned to receive azacitidine alone or azacitidine in combination with DLI based on current risk. Patients may receive up to 6 additional courses of azacitidine with or without DLI after withdrawal of immunosuppression; the addition of DLI will be guided by risk assessments done prior to each subsequent course.

Low Risk:

- Pre-Transplant Deep Sequencing (DS) MRD AND Post-Transplant DS- MRD negative ($<10^{-6}$)

Standard Risk:

- Active Grade I GVHD, OR
- Any history of >Grade II GVHD, OR
- Full Donor Chimerism AND Pre-HSCT MRD-neg AND Post-HSCT MRD-neg

High Risk:

- No GVHD or resolved Grade I GVHD, AND
- Mixed chimerism OR Pre-Tx MRD(+) OR Post-Tx MRD(+)

[figure not shown]

Figure 1b: Schema for acute lymphoblastic leukemia. Patients will be enrolled on study prior to Day +28. Chimerism from PB and BM as well as MRD (by conventional flow cytometry as well as deep sequencing when available) will be assessed. Patients with Grade III-IV GVHD will not receive study immunomodulatory therapy. Patients meeting criteria for High-Risk designation will receive azacitidine followed by fast withdrawal of immunosuppression. Standard-Risk patients will receive azacitidine with standard withdrawal of immunosuppression. Low-Risk patients will not receive study immunomodulatory intervention and will be treated per local SOP. Risk assessment will be completed following withdrawal of immunosuppression, and patients will be assigned to receive standard therapy, azacitidine alone, or azacitidine in combination with DLI based on current risk. Patients may receive up to 6 additional courses of azacitidine with or without DLI after withdrawal of immunosuppression; the addition of DLI will be guided by risk assessments done prior to each subsequent course.

Table of Contents

Section No.		Page No.
1.0	Background and Rationale.....	10

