3.0 Study Design and Eligibility Criteria

3.1 Study Design (see also Study Schema, page 3)

- 3.1.1 We propose a Phase II single-arm trial of azacitidine (IV or SC) in combination with escalating donor lymphocyte infusions (DLI). This study will be open to patients with ALL, AML, JMML, or MDS.
- 3.1.2 The first cycle of azacitidine will be administered during withdrawal of immunosuppression for patients not developing severe organ toxicity or Grade III-IV GVHD.
- 3.1.3 After the initial cycle during withdrawal of immunosuppression (duration is based on day 28 PB chimerism), azacitidine is given for 4 days in 6-week cycles (+/- 2 weeks) at a dose of 40 mg/m²/day.
- 3.1.4 For patients meeting High Risk criteria who have available cell product, DLI is given on day 5 of each cycle in escalating doses. Peripheral blood chimerism and MRD is assessed after week 4, prior to initiating the next cycle. BM chimerism and MRD is

obtained at regular intervals prior to specified cycles as per the study schedule. Patients will receive up to 7 cycles as tolerated.

3.1.5 Patients will be followed by laboratory monitoring and physician evaluation prior to each cycle. Weekly labs will be obtained and will include toxicity monitoring (CBC, LFTs, and electrolytes) and correlative studies, such as immunophenotype and T cell function by PHA. Patients will be followed for two years to study toxicity and GVHD outcomes as well as relapse incidence.

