8.4 Sample size

- 8.4.1 The sample size is estimated using Bayesian sequential monitoring design with toxicity and response outcomes as multiple endpoints(45). It is assumed that the rate of relapse in pediatric acute leukemia post-transplant would be 40% (as shown in our pilot study), azacitidine +/- DLI would reduce the 2-year relapse rate by approximately 40% to a rate of 25%. A sample size of 67 evaluable patients is required to provide 80% power at a one-sided significance level of 0.05 to test the hypothesis based on the relapse rate of H0: relapse rate > 40% (historically-controlled) versus Ha: relapse rate < 25% (treatment-targeted). The study will enroll patients until accrual of 67 patients is achieved.
- 8.4.2 Enrollment of 67 patients will be attainable with enrollment at multiple centers. Investigators from All Children's Hospital, Lucille Packard Children's Hospital have written letters of support expecting to enroll 30-40 patients over 2 years.

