8.7 Interim analysis and stopping rules for safety and efficacy

- 8.7.1 As a phase II study with 67 evaluable patients, the study is designed to have interim stopping rules based on the safety/toxicity evaluation (including death and incidence of severe GVHD). See Section 11.0 for reporting SAEs associated with study stopping rules.
- 8.7.2 The occurrence of any serious adverse events (SAEs) will be reported to the Coordinating Trial Center within 24 hours of learning about them, and within 10 days in writing. See Section 11.0 for SAE definitions and reporting requirements. A rate of SAEs of up to 20% is deemed acceptable in view of the potential benefit of the therapy. Accrual will stop if 3 patients with SAEs are observed in the first 3-6 patients undergoing the intervention, if 4 patients with SAEs are observed in the first 7-9 patients undergoing the intervention, or if 5 patients with SAEs are observed in the first 10-13 patients undergoing the intervention. The following table displays the minimum

number of SAEs for the study to be stopped at each accrual period and the probability of early stopping at the assumed SAE rate.

Patients on Study	4-6	7-9	10-13	14-17	18-21	22-27
Number of patients with SAE	≥3	≥4	≥5	≥6	≥7	≥8
15%SAE	1.2%- 4.2%	1.1%- 2.8%	0.9%- 2.7%	0.9%- 2.4%	0.9%- 2.0%	0.8%- 2.6%
20%SAE	2.6%- 8.2%	2.9%- 6.6%	2.6%- 6.9%	3.2%- 6.8%	3.5%- 6.6%	3.6%- 8.2%
25%SAE	4.7%- 13.2%	5.8%- 11.7%	5.8%- 12.6%	7.3%- 12.8%	8.2%- 12.7%	8.9%- 14.2%

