8.7.3 Stopping rules for interim toxicity and relapse futility

- Study data will be analyzed for relapse rates within 3 months for efficacy assessment. Such early futility assessment will be done when the first 14 patients have completed the 3-month follow-up in the study. If there are 9 or more relapses out of 14 patients during the futility assessment, enrollment will be stopped due to futility. Otherwise an additional 54 patients will be accrued for a total of 67 patients in the study. By the end of the study, if there are 32 or more relapses observed, further investigation will not proceed. In this study the rate of relapse in pediatric acute leukemia post-transplant is assumed to be 40% (as shown in our pilot study), azacitidine +/- DLI would reduce the 2-year relapse rate by approximately 40% to a rate of 25% and that the toxicity rate in pediatric acute leukemia post-transplant under azacitidine +/- DLI would be 20%. The stopping rules for toxicity and relapse rate under sequential design of multiple endpoints are shown below:
- For patients receiving DLI, a subset analysis of incidence of Grade III-IV aGVHD and mortality secondary to GVHD will be performed when a new patient is diagnosed with Grade III-IV GVHD or chronic GVHD.
 - Reported rates of grade III-IV acute GVHD following DLI range from 20-35%; GVHD-related mortality ranges from 5-15%.
 - If rates of Grade III-IV aGVHD or GVHD-related mortality in this study exceed published rates, enrollment and further DLI administration will be suspended while further safety analysis is performed.

Patients on Study	<14	15-21	22-28	29-35	36-42	43-49	50-56	57-63
Number of patients with SAE (Toxicity)	>8	≥10	≥13	≥16	≥18	≥21	≥23	≥26
Number of patients with relapse in 3 months	>9	≥13	≥16	≥19	≥23	≥26	≥29	≥32

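### The summary's success rule puts both cut-offs at the plan's own assumed rates, so a treatment performing as planned would usually miss it, and the 80% power does not describe that rule

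*Combined protocol and SAP*

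**What the plan says.** The only explicit definition of success is in the protocol summary. It has two parts: "The study will be considered successful if the rate of relapse at 2 years is" below 25%, "and the incidence of Grade IV GVHD and severe drug toxicity are" below 20%.

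Section 8.4.1 names the design: "The sample size is estimated using Bayesian sequential monitoring design with toxicity and response outcomes as multiple endpoints". It takes 40% relapse as the historical rate and 25% as the target. It then states: "A sample size of 67 evaluable patients is required to provide 80% power at a one-sided significance level of 0.05", with both hypotheses written as relapse rates.

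Section 8.7.3 repeats the relapse assumptions and adds that "the toxicity rate in pediatric acute leukemia post-transplant under azacitidine +/- DLI would be 20"%. It also sets an end-of-study cut-off: with 32 or more relapses, further investigation stops. Section 8.7.2 says: "A rate of SAEs of up to 20% is deemed acceptable in view of the potential benefit of the therapy".

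Section 8.6.2 plans to estimate the primary endpoints as proportions with 95% confidence intervals. No section gives the probability of meeting the two-part success rule, or an error rate for its safety half.

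**The concern.** A success cut-off equal to the rate expected under the treatment is met about half the time, whatever the sample size. Here both halves of the rule are built that way, and both must be met. A treatment that does exactly what the plan hopes for would then more often be called unsuccessful than successful.

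The plan also leaves three relapse standards side by side: the summary's 25%, the cut-off implied by the powered test, and the 32-relapse limit in 8.7.3. The only power figure offered belongs to the second. Someone who reads the success definition and then the 80% has no way to see that the two do not go together.

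**Working it through.** **Inputs.** N = 67, one-sided alpha 0.05, power 80%, relapse 40% versus 25% (8.4.1). Toxicity 20% (8.7.3). Success limits of 25% and 20% (summary).

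**Step 1: reproduce the plan's figure.** The one-sample normal approximation is n = [z(0.95)·√(p0·q0) + z(0.80)·√(p1·q1)]² / (p0 − p1)². This gives [1.645 × 0.490 + 0.842 × 0.433]² / 0.15² = 60.9. With a continuity correction it is 67.4, in line with 67. By exact binomial at n = 67, the largest relapse count that rejects 40% at one-sided 0.05 is 19:

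- P(X ≤ 19 | 0.40) = 0.032 (alpha)
- P(X ≤ 19 | 0.25) = 0.784 (power)
- X ≤ 20 would have alpha 0.056

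So 67 and roughly 80% hold for relapse alone.

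**Step 2: turn the success rule into counts.** 0.25 × 67 = 16.75, so relapse below 25% means at most 16. 0.20 × 67 = 13.4, so toxicity below 20% means at most 13 (13/67 = 19.4%; 14/67 = 20.9%).

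**Step 3: each half at the planning rates.**

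- Relapse: P(X ≤ 16 | 0.25) = 0.481
- Safety: P(T ≤ 13 | 0.20) = 0.524

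For an 80% chance on its own half, the true relapse rate would have to be about 20.5%, and the true toxicity rate about 16.4%.

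**Step 4: both halves together.**

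- Observed-rate rule, independence: 0.481 × 0.524 = 0.252. Under any dependence the range runs from 0.481 + 0.524 − 1 = 0.006 (unrounded inputs) to the smaller of the two, 0.481.
- Relapse by the powered test (at most 19), independence: 0.784 × 0.524 = 0.411. Range 0.308 to 0.524.

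Neither reading reaches 80% at the planning rates, even at its upper bound. If the 8.7.2 stopping boundaries are applied as well, and a stopped trial counts as not successful, simulation lowers the 0.252 to about 0.23.

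**Step 5: sensitivity to the true rate of the safety endpoint** (true relapse 25%, independence).

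| True toxicity | Safety half met (≤ 13) | Both, relapse ≤ 16 | Both, relapse ≤ 19 |
|---|---|---|---|
| 10% | 0.994 | 0.479 | 0.779 |
| 15% | 0.879 | 0.423 | 0.689 |
| 18% | 0.686 | 0.330 | 0.538 |
| 20% | 0.524 | 0.252 | 0.411 |
| 25% | 0.181 | 0.087 | 0.141 |

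The first row shows that the shortfall is not only a safety matter. With toxicity at 10%, the observed-rate rule is still met less than half the time, because the relapse half caps it at 0.481.

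**Step 6: the 32-relapse limit.** 32/67 = 47.8%. P(X ≤ 31 | 0.40) = 0.879, so most trials at the historical rate would stay under it. It agrees with neither 16 nor 19.

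**The case against.** Several points on the other side stand.

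- **A reader might infer that the protocol claims 80% power for overall success.** It does not. Section 8.4.1 ties the figure to the relapse hypothesis. The fault is a missing operating characteristic and a success rule that does not match the test, not a wrong power calculation.
- **A reader might infer that the safety half is simply a coin flip.** That needs the success endpoint to have the 20% rate. The 20% in 8.7.3 is for toxicity, tabulated there as SAEs, and 8.7.2 sets a ceiling on SAEs. The summary names Grade IV GVHD and severe drug toxicity, while the stopping-rule events in 11.16 also include severe chronic GVHD and related death. If the success endpoint is narrower, its rate may be under 20%. The summary's plural verb may also mean that each component is judged separately, and the documents give no component rates.
- **The denominator is not settled.** The 20% is a rate under azacitidine with or without DLI. Low-Risk ALL patients receive neither (5.7.6, 5.8.1), and evaluable is not defined.
- **The summary does not say that the rates are observed ones.** That reading is an inference, supported by 8.6.2. Requiring a confidence limit to lie below the cut-off would be harder to pass, so it would not rescue the 80%.
- **Independence is an assumption.** The rationale links graft-versus-leukemia effect and GVHD, so the bounds in the working matter.
- **Safety has some stated operating characteristics.** Section 8.7.2 tabulates early-stopping probabilities at 15%, 20% and 25%. They govern accrual and do not describe the success rule.

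It is also tempting to rescue the safety half with a looser limit tested against 35%, the top of the range quoted in 8.7.3. That range is for Grade III-IV acute GVHD after DLI, which is a different event in a subset of patients. A limit of 16 of 67 would pass 48% of trials with a true 25% rate.

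**Conclusion.** The concern holds for the success rule as written. Both cut-offs sit at the plan's assumed rates. Read as observed proportions in 67 patients, the halves are met with probability 0.48 and 0.52, and both with probability about 0.25 under independence and at most 0.48 under any dependence. With relapse judged by the powered test, the joint figure is about 0.41.

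The relapse half of this conclusion rests only on reading the rule as an observed rate. The safety half also needs the 20% to apply to the success endpoint in all 67 patients; at 15% or 10% it is met 88% or 99% of the time. No single overall success probability can therefore be quoted as the trial's.

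The sample size and the 80% (exact 78%) are sound for relapse alone. The documents do not support reading this as a sample-size error, or as a fault of the safety criterion only.

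**What to change.** - **Summary, relapse:** replace the 25% limit with the cut-off of the powered test: the 40% null is rejected, at most 19 relapses in 67. Reconcile this with the 32-relapse limit in 8.7.3, so that one end-of-study relapse rule remains or the separate purpose of each is stated.
- **Summary, safety:** state which events and which patients the 20% criterion covers, and whether it applies to the components jointly or separately. Reconcile a limit strictly below 20% with 8.7.2, which accepts a rate of exactly 20%.
- **8.4.1:** say that the 80% (exact 78%) is for the relapse test only. Give the probability of meeting both criteria over a range of true toxicity rates, for example 10% to 25% as in the table above, with the independence assumption stated.
- **8.6.2:** name the decision rule applied to the estimated proportions.

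The cost is wording in these sections and no extra patients. The drawback is that the stated chance of overall success will look less favourable than 80%.

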1.0 Background and Rationale

1.1 Prevention of relapse in pediatric hematologic malignancies

Multiple hematologic malignancies, such as acute myeloid leukemia (AML), acute lymphoblastic leukemia (ALL), juvenile myelomonocytic leukemia (JMML) and myelodysplastic syndrome (MDS) are treated with myeloablative hematopoietic stem cell transplantation (HSCT) in order to safely deliver high doses of anti-neoplastic therapy, and to take advantage of donor-derived immune cells to produce an allogeneic “graft-versus-leukemia” effect. As conditioning regimens and supportive care measures improve, transplant-related morbidity and mortality have decreased, such that relapse is the primary cause of treatment failure in these patients. Recent data for pediatric ALL, AML, and JMML demonstrate a 5-year relapse rate of 30-40% (1-3). Survival rates in patients who relapse following transplant are <20% at 4 years (4).

Additional strategies for the prevention of post-transplant relapse are needed. This study combines minimal residual disease by high throughput sequencing, multiparametric flow MRD, and donor chimerism to direct the application of post-transplant immunomodulatory therapy with azacitidine and donor lymphocyte infusion (DLI). By administering this therapy to patients at highest risk of relapse, this study aims to decrease relapse rates while maintaining a low risk of GVHD.

1.2 Predictors of post-transplant relapse

Mixed chimerism (MC) is the presence of both host's and donor's hematopoietic cells after allogeneic transplant. With the introduction of quantitative and frequent measurements of chimerism, the relationship between the presence of host cells and the relapse of acute leukemias after allogeneic transplant was recognized. In 1998, Bader et al. showed that pediatric patients with increasing amount of host (autologous) cells on their chimerism testing following allogeneic transplant have significantly increased risk of relapse (5). In their study, 36/54 children had complete donor chimerism and 19% of them relapsed, 10/54 children had increasing amounts of host cells post-transplant (increasing host chimerism) and 90% of them relapsed; in contrast, 8/54 children had decreasing amount of host cells following transplant (decreasing host chimerism) and none of them relapsed (5). Similar results were obtained by Barrios et al. in adults; 93% of patients with increasing host chimerism and 27% of patients with full donor chimerism relapsed, respectively (6).

Patients with increasing host chimerism sustained relapses between days 36 and 450 of their follow-up. Increasing host chimerism preceded relapse by a median of 74 days (6). The investigators concluded that frequent and sensitive measurement of chimerism after transplant is a useful tool for identifying a group of patients with a very high risk of relapse in whom further immunotherapy would be justified. Additionally, Bader and colleagues studied the origin of cells found in patients with mixed chimerism. In the early post-transplant period, mixed chimerism was caused predominantly by normal recipient hematopoietic cells. This finding supports the hypothesis that a state of mixed hematopoietic chimerism may reduce the clinical GVL effect of alloreactive donor-derived effector cells in patients with acute leukemias, and thus facilitate the proliferation of residual malignant cells that may have survived the preparative regimen (7).

The presence of minimal residual disease (MRD), either immediately prior to HSCT, or following HSCT, has been correlated with decreased survival and increased risk of relapse in both ALL (8) AML (9) patients (10). An MRD-guided strategy of reduction of immunosuppression without DLI or azacitidine resulted in overall survival of 72% in patients with MRD <0.1%, and 40.4% in those with MRD>0.1% (11). This protocol plans to build on

this approach through risk stratification based on MRD and chimerism, and post-transplant immunomodulation with not only fast withdrawal of immunosuppression, but also azacitidine and escalating doses of DLI.

1.3 Calcineurin inhibitor dose manipulation as a form of immunotherapy

In a randomized study that looked at the effect of dose of cyclosporine A (CSA) on leukemia relapse after transplant, disease-free survival was superior in patients receiving low dose CSA (1mg/kg/day) than in those receiving high dose CSA (5 mg/kg/day) (12). This benefit of low dose CSA persisted 10-years after transplant, but only in patients younger than 30 years of age, as the older patients receiving low CSA dose had an increased risk of transplant-related complications (13). A similar study in children comparing 1 mg/kg/day of CSA vs. 3 mg/kg/day showed relapse rates of 15% vs. 41% in low and high CSA dose groups, respectively (14). A study looking into the length of treatment with CSA (60 vs. 180 days) indicated that CSA can be safely stopped at 60 days in patients who did not have evidence of acute GVHD (15).

1.4 DLI as a form of immunotherapy

Donor lymphocyte infusions have been successfully used in patients with chronic myelogenous leukemia who relapse after transplant (16, 17). However, DLI is far less successful when given to acute leukemia patients who relapse after transplant. While the remission induction rate with DLI for CML is 80% and the effect appears to be prolonged, the remission induction rate for patients with acute leukemia is 15 – 25%, and often is of short duration (18). The failure of donor lymphocytes in the acute leukemia setting may be due to inadequate graft vs. leukemia effect in the presence of clinical relapse with a large leukemic cell burden. In order to avoid a large leukemic cell burden, investigators have moved to pre-emptive use of DLI in patients at a high risk for relapse. DLI have been extensively used in the setting of non-myeloablative or reduced toxicity transplantation (19, 20).

